## **Sample size calculation and estimated duration of the study**

Sample size calculation is based on the incidence of NEC, as the rarest of the events that will be studied, which is currently about 15% among extremely preterm infants at our unit, as mentioned above. For study power of at least 70%, confidence level of 5%, and an expected decrease of NEC incidence from 15% to 8%, each study arm should include about 100 participants (29). Each year, our unit treats about 70 infants born in GA 22+0 – 26+6. Supposing a participation rate of 70%, it is estimated that the recruitment period should last between 3 and 4 years, preliminarily starting during 2018. However, a recruitment period of maximum 5 years will be allowed.

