### **Completion of the study**

The study will be completed when the number of 100 subjects per study arm is reached (a maximum of 130 subjects per study arm will be allowed), estimated to be achieved by the year 2022 (and not later than year 2023).

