### **Statistical analysis**

Numerical data with a gaussian distribution will be expressed as means (standard deviation), otherwise as medians (ranges). We will use the Anderson-Darling test to assess the normality of the data. Numerical values will be compared between intervention and control groups using t-tests or the Mann-Whitney U test. Categorical variables will be compared using  $\chi^2$  or Fisher's exact tests. Times to achieve full enteral feeding will be compared by the log rank test. Multiple Cox regression analysis will be used to adjust for covariates, such as gestational age and birth weight. IBM SPSS software (current version at the time of publication) will be used for all calculations and a p-value of <0,05 will be considered significant.

Interim analysis will be conducted when 35 infants have been recruited in each study arm (estimated about 1,5 years from study start). Another interim analysis will be conducted when 65 infants have been recruited in each study arm (estimated about 3 years from study start). Unplanned interim analysis will also be conducted in case of subjectively estimated too obvious difference between the groups regarding the primary outcomes, at any time during the study. The study will be discontinued as soon as an interim analysis shows statistically significant results regarding the primary outcomes or severe adverse events.

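### The sample size section claims at least 70% power for NEC, but its own inputs with 100 infants per arm give about 35%

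*Combined protocol and SAP*

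**What the plan says.** The protocol's section on sample size and study duration bases the number of infants on NEC, as the rarest event to be studied. The control rate is one "which is currently about 15% among extremely preterm infants at our unit". The planning assumptions are "study power of at least 70%, confidence level of 5%, and an expected decrease of NEC incidence from 15% to 8"%, from which it follows that "each study arm should include about 100 participants". The only source given is an online calculator. Sidedness, formula and allowance for dropout are not stated.

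Other sections supply the rest:

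- *Allocation*: randomization is 1:1.
- *Primary outcomes*: NEC of Bell stage II or more is primary, together with time to full enteral feeding (TFF).
- *Completion of the study*: the target of 100 per arm is repeated, and "a maximum of 130 subjects per study arm will be allowed".
- *Statistical analysis*: categorical outcomes are compared by chi-square or Fisher's exact test, and "a p-value of <0,05 will be considered significant".

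No power calculation is given for TFF.

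**The concern.** Lowering an event rate from 15% to 8% is a difference of 7 percentage points. With 100 infants per arm, that is 15 expected cases against 8. The standard error of the difference is about 4.5 points, so the expected z-statistic is only about 1.6, below the two-sided critical value of 1.96. Power must therefore be under one half, and 70% cannot be right.

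This is the trial's only power statement. Told that power is at least 70%, a reader would expect a true effect of the assumed size to be missed at most three times in ten, and could give a non-significant NEC result more weight against benefit than it deserves. The ethics board and parents also rely on a correct account of what the trial can show.

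**Working it through.** **Inputs.** Control rate p1 = 0.15, intervention rate p2 = 0.08 and about 100 per arm (sample size section); ceiling of 130 per arm (*Completion of the study*); level 0.05 and chi-square or Fisher test (*Statistical analysis*); 1:1 allocation (*Allocation*). Sidedness is not stated, so both readings are tried.

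**Step 1: try to reproduce the plan's figure.** The per-arm size for 70% power, with p̄ = (0.15 + 0.08)/2 = 0.115, is

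n = [z_α √(2p̄(1−p̄)) + z_β √(p1(1−p1) + p2(1−p2))]² / (p1−p2)²

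- √(2 × 0.115 × 0.885) = 0.4512
- √(0.1275 + 0.0736) = 0.4484
- z_β = 0.524 for 70% power

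Two-sided: (1.960 × 0.4512 + 0.524 × 0.4484)² / 0.0049 = 255.7, so **256 per arm**.

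One-sided: (1.645 × 0.4512 + 0.524 × 0.4484)² / 0.0049 = 194.9, so **195 per arm**.

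A continuity correction raises these to 284 and 223; unpooled variance gives 254 and 194. The stated figure of about 100 is not reproduced by any of them.

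**Step 2: power at the stated size.** Power = Φ{[(p1−p2) − z_α √(2p̄(1−p̄)/n)] / √[(p1(1−p1) + p2(1−p2))/n]}.

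For n = 100, two-sided: (0.07 − 1.960 × 0.04512) / 0.04484 = −0.411, and Φ(−0.411) = 0.341.

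| Test, 5% level | 100 per arm | 130 per arm |
|---|---|---|
| Two-sided, normal approximation | 34.1% | 42.4% |
| Two-sided chi-square, exact enumeration | 34.7% | 42.6% |
| Two-sided Fisher, exact enumeration | 27.0% | 35.4% |
| One-sided, normal approximation | 46.3% | 55.0% |

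Unpooled and arcsine versions at 100 per arm, two-sided, give 34.5% and 34.8%.

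**Step 3: what would make 70% true at 100 per arm.** Keeping the effect, the two-sided significance level would have to be about 0.30 (power 69.8%). Keeping the two-sided 5% level, NEC would have to fall from 15% to about 4.6%.

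**Step 4: the interim looks.** *Statistical analysis* plans looks at 35 and 65 per arm, with stopping on significance and no stated adjustment. Simulating unadjusted two-sided chi-square tests at 35, 65 and 100 per arm gives a 42% chance of any significant NEC result. A further look at 130 gives 52%. With NEC at 15% in both arms, the same schedules give false-positive rates of about 11% and 13%.

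**The case against.** The strongest points on the other side are these.

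- *Sidedness is unstated.* True, so the 35% figure rests on a two-sided reading. The most favourable reading, one-sided and uncorrected, still gives only 46%.
- *The size is approximate and may grow to 130.* The requirement is about twice (one-sided) to two and a half times (two-sided) the stated size, and 130 falls short under every test in the table.
- *Missing the effect two times in three describes one final analysis.* This stands as a qualification. With the planned looks the miss rate is about 58%, or 48% with a further look at 130. That gain comes from an inflated type I error, and power is still well below 70%.
- *TFF is also primary.* Low power for NEC does not defeat the TFF question. But the plan sizes the trial on NEC alone and gives no TFF assumptions, so TFF cannot support the stated figure.
- *A larger trial is out of reach.* At 70 infants a year, 70% participation and five years at most, 70 × 0.70 × 5 = 245 infants can be recruited, against 2 × 256 = 512 needed. This stands, and it is why the remedy is disclosure and not enlargement.

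The protocol does not commit the investigators to reading a null NEC result as absence of benefit; that is a risk, not something the plan says.

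**Conclusion.** The power statement is wrong as written. For NEC at 15% against 8% with 100 infants per arm, power is about 35% by two-sided 5% chi-square, 27% by Fisher's exact test, and 46% at best if a one-sided 5% test was meant. The claim of at least 70% is therefore about double the two-sided figure. The conclusion uses the plan's own rates, level and size; the one assumption added is sidedness, and neither choice rescues the claim. Nothing elsewhere in the protocol supplies an assumption that would close the gap. How the figure of 100 arose cannot be established from the document. This must be corrected, because the trial is sized on it.

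**What to change.** Replace the power sentence with one the inputs support, for example:

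> With 100 infants per arm, power is about 35% (two-sided 5%, chi-square test) for NEC of 15% versus 8%; 70% power is reached only for 15% versus about 4.6%.

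In addition:

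- State sidedness, and which test (chi-square or Fisher) is primary for NEC.
- Commit to reporting NEC as a risk difference with a 95% confidence interval, and to not reading non-significance as no effect.
- Add a power statement for TFF using the unit's own expected proportion reaching full feeds and a target hazard ratio. The protocol gives neither, so the following is illustration only. If 90% of 200 infants reach full feeds (180 events), two-sided 5% power is about 80% for a hazard ratio of 1.52, since 4(1.96 + 0.842)²/(ln 1.52)² = 179 events, and about 78% for 1.50. If 80% to 100% do (160 to 200 events), power for 1.50 runs from 73% to 82%. If the 5% level were split equally over the two primary outcomes, 180 events would give about 68% for 1.50.

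The cost is rewording one section and a short addition to the analysis section. The stated power becomes less favourable; no extra patients are needed.

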## **Eligibility criteria**

All infants born extremely preterm in GA between 22+0 and 26+6 weeks at the NICU of University Children's Hospital in Uppsala will be consecutively recruited in the study during the years 2018 – 2022. Written informed consent will be obtained from both parents before enrollment in the study.

## **Exclusion criteria**

Infants with major dysmorphic features and major congenital anomalies, such as gastrointestinal disorders, as well as infants with circulatory instability during the first hours of life will be excluded from the study.

## **Feeding regimen and feeding intolerance guidelines (common for both groups)**

### Feeding regimen:

All infants born between GA 22+0 and 26+6 are fed exclusively with breast milk (mother's and/or donated), the first feeding given as soon as possible after birth (usually within one to two hours) and then 2-hourly. At day 1, the following scheme is applied:

- GA 26 – 28 v: total volume 80-90 ml/kg/day; enteral nutrition 2ml/kg every two hours, and the remaining is administered as PN through a central venous access.
- GA <26 v: total volume 90-100 ml/kg/day; enteral nutrition 1ml/kg every two hours, and the remaining is administered as PN through a central venous access.

The total feeding volume is advanced progressively on an individual basis, usually by 10-20ml/kg/day, to a final volume between 150 and 200ml/kg/day, striving not to exceed a weight loss of 10%, and depending on feeding tolerance. Full enteral nutrition is pursued within 5 days for GA 26 – 28 weeks and within 7-10 days for GA ≤26 weeks. PN is discontinued when enteral feeding reaches about 150 - 200 ml/kg/day, considering the child's growth development. Protein fortification is usually initiated when enteral nutrition constitutes more than 75-100 ml/kg/d (~50%) of total fluid volume.

### Feeding intolerance:

In case of feeding intolerance, the feeding strategy is modified accordingly, depending on the nature and severity of symptoms.

Specific symptoms that should lead to continued treatment:

- In case of occasional vomiting and / or biliary retention without any other symptoms, the position of the nasogastric catheter is checked, a clinical assessment is performed and EN is eventually withheld or reduced. One must specifically consider the potential onset of infection or gastrointestinal disease such as NEC, intestinal obstruction etc. Depending on the course of symptoms, the same or reduced food volume is continued.
- In case of more severe symptoms, such as cardio-respiratory instability, impaired abdominal status (e.g. inflated abdomen, abdominal pain) in combination with repeated vomiting, bilious

residuals or lack of defecation, EN is withheld, paediatric surgeon is consulted and radiological and laboratory investigation including early treatment with antibiotics (tazobactam / piperacillin + gentamicin) is considered. If NEC and / or sepsis diagnosis is not established / suspected and the child continues to show signs of food intolerance, fasting should continue for at least 24 hours and the clinical status carefully monitored with repeated laboratory / radiological assessment. EN is resumed when symptoms have passed / are ameliorated and most importantly infection / NEC has been ruled out.

### **Intervention**

The following intervention will be applied to the intervention group: specially trained pediatric surgeon will administer 10ml/kg pre-warmed (37°C) normal saline via a single-use rectal tube of size 6FR twice per day, aiming at a depth of maximum 10 cm/kg, starting after randomization and not later than 24 hours of age, and continued until full enteral nutrition of 170ml/kg/day is achieved or NEC diagnosis (Bell stage II or more) is established, whichever comes first. However, the intervention will be applied at a maximum of 2 weeks from birth. Besides, the intervention will be withheld in case of suspicion of infection or NEC but will be resumed if antibiotics are not introduced and discontinuation of feeds does not exceed 48 hours. Early stopping criteria include infection / sepsis or NEC suspicion necessitating prolonged discontinuation of feeds > 48 hours and / or antibiotics, circulatory instability or adverse events. The intervention will only be applied at the NICU of University Children's Hospital in Uppsala and will be discontinued if the infant is transferred to another hospital. Standard departmental guidelines will be followed regarding ventilation, choice of PN, invasive monitoring, and management of sepsis and/or necrotizing enterocolitis (NEC) for both the intervention and the control groups.

### **Comparison group**

The following guidelines are currently applied at our unit for extremely preterm infants that do not defecate adequately:

If the child has not passed meconium or has already passed meconium / feces but has not defecated for 3-4 days:

- If there are no symptoms: continued EN, follow-up of clinical status and defecation pattern. If the child has not defecated for another 1-2 days (and remains asymptomatic), consider the following treatment strategy to facilitate defecation:
  1. Tactile perineal stimulation is performed by a nurse, using a room temperature damp compress
  2. Cautious rectal stimulation is performed by a nurse, using a rectal catheter size 6FR; depth 1 - 2 cm
  3. Step 1 & 2 is repeated depending on effect and defecation pattern
  4. If Step 1 & 2 does not result in defecation and the clinical status is unchanged, enema with 4mL / kg sodium chloride 9mg / mL is given
  5. In case of no effect, a pediatric surgeon is consulted, and consideration is given to continued treatment; (1) watchful waiting alternatively repeated enema (2) rectal washout with 10 mL / kg sodium chloride 9mg / mL (3) further radiological and laboratory investigations
- In case of symptoms (cardiorespiratory instability, impaired abdominal status, vomiting, bilious residuals, etc.): EN is withheld, pediatric surgeon is consulted and radiological / laboratory investigations as well as early treatment with antibiotics (tazobactam / piperacilline + gentamicin) is considered.

Glycerin suppositories / enemas are not used at our unit.

### Primary outcomes

- TFF, defined as the period between birth and achievement of enteral nutrition of 170ml/kg/d.
- NEC, Bell stage II or more

## **Secondary outcomes**

Time to regaining of birth weight, growth, BPD, IVH, PDA, ROP, small intestinal perforation, sepsis, hyperbilirubinemia, mortality, adverse events, age at the time of discharge from hospital, number of days on PN, IFALD, and neurological development.

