## **Follow-up**

All extremely preterm infants hospitalized in our unit are discharged home at about GA 35+0. Infants regionally belonging to another hospital are usually transferred to the “home hospital unit” not earlier than GA 28+0. After hospital discharge, all extremely preterm infants are routinely followed-up according to a nationwide schedule, until the age of 5,5 years. Data mostly concerning children’s growth as well as neurological and psychomotor development are collected, and interventions are made as needed.

Study participants will be followed-up until full term corrected age (GA 40 +0), and medical information including possible treatments as well as diagnosis of NEC or other gastrointestinal complication, sepsis, PDA, BPD, ROP, IVH, hyperbilirubinemia, growth parameters (weight, length, head circumference) and mortality will be collected by the investigators from the treating physicians and electronic medical records. All the clinical, laboratory and radiological findings of infants treated at our unit are routinely and continuously registered in detail, with the use of medical computer software, during the whole hospitalization period, and these data will be readily accessible to the investigators. Besides, data on children’s growth and neurological development will be collected from the electronic medical records, until the age of 5,5 years. The above-mentioned data of study participants that have been transferred to the home or other hospital unit will be collected by the investigators though communication with the treating physician at the respective hospital.

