The intervention will be discontinued if the infant is transferred to another hospital, as mentioned before. The decision to transfer a study subject to home or other hospital unit will only be based on current criteria and will not be affected by the participation in the study. Study participation is not expected to delay the transfer to home hospital and prolong the stay at our NICU in Uppsala, unless a severe adverse event should occur.

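### Age at discharge is not defined; read as postnatal age it keeps the spread due to gestational age at birth, which costs precision but does not bias the comparison

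*Combined protocol and SAP*

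**What the plan says.** The Secondary outcomes section names "age at the time of discharge from hospital" in a list and adds nothing about the age scale, the event that ends the period, or infants who die before leaving hospital.

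Follow-up gives the timing: "All extremely preterm infants hospitalized in our unit are discharged home at about GA 35+0". It treats movement to another unit as a separate event: "Infants regionally belonging to another hospital are usually transferred" to their home unit, "not earlier than GA 28+0". The same section says that data on transferred infants will be obtained from the treating physician at the receiving hospital. Its list of items to collect does not include the date of discharge home.

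Eligibility covers "All infants born extremely preterm in GA between 22+0 and 26+6 weeks". The Allocation section describes 1:1 randomisation and states no stratification by gestational age or home region.

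Under Statistical analysis, "Numerical values will be compared between intervention and control groups using t-tests or the Mann-Whitney U test". Two sentences after that rule, directly after the log-rank test for time to full feeds, comes "Multiple Cox regression analysis will be used to adjust for covariates, such as gestational age and birth weight". No outcome is named in that sentence, and home region is not among the covariates mentioned.

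**The concern.** Taken without qualification, an infant's age at discharge is normally read as days since birth. If infants go home at roughly one postmenstrual age, days since birth are roughly that age minus gestational age at birth. Part of the variation in the outcome is then fixed before randomisation and unrelated to the lavage, and an unadjusted two-sample test counts it as noise.

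The protocol's summary and background link feeding failure to longer hospital stays, so this outcome bears on part of the rationale. At stake is sensitivity: a null result could partly reflect the mix of gestational ages. There is also a reproducibility problem, since two analysts could build different endpoints from the same infants (postnatal or postmenstrual age; leaving Uppsala or going home). For a transferred infant, the date needed for discharge home is not on the collection list.

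**Working it through.** **The plan's own figure.** There is none to reproduce. The documents give no expected effect, SD or power for age at discharge; the only sample-size calculation is for NEC. About 100 infants per arm (sample size section) is used below.

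**Calendar arithmetic (from Eligibility criteria and Follow-up).** Postnatal age at discharge home = GA at discharge − GA at birth.
- Born 22+0: 35+0 − 22+0 = 13 weeks = 91 days.
- Born 26+6: 35+0 − 26+6 = 8 weeks 1 day = 57 days.
- Spread from gestational age alone: 91 − 57 = 34 days.

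The range covers 35 possible birth days. If births are uniform over them (assumed), SD = √((35² − 1)/12) = 10.1 days. If weighted linearly toward later gestation (assumed), SD is about 8.4 days.

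**Share of variance due to gestational age.** Share = 10.1² / (10.1² + r²), where r is the SD of all other variation in discharge timing. The documents do not give r, so a range is shown. The total SD without adjustment is √(10.1² + r²).

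**Power.** Two-sided 5% t-test, 100 per arm, assumed difference of 5 days, standard error = SD × √(2/100).

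| Other SD (r) | Share from GA | Total SD | 5 / SE, GA left in | Power, GA left in | 5 / SE, GA removed | Power, GA removed |
|---|---|---|---|---|---|---|
| 10 | 50% | 14.2 | 5/2.01 = 2.49 | 70% | 5/1.41 = 3.54 | 94% |
| 14 | 34% | 17.3 | 5/2.44 = 2.05 | 53% | 5/1.98 = 2.53 | 71% |
| 21 | 19% | 23.3 | 5/3.30 = 1.52 | 33% | 5/2.97 = 1.68 | 39% |

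With the later-weighted distribution (SD 8.4) the loss is somewhat smaller. Total SD is √(14² + 8.4²) = 16.3, giving power of about 58% at r = 14, and √(10² + 8.4²) = 13.1, giving about 77% at r = 10.

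**Chance imbalance.** The difference between arms in mean gestational age has a standard error of 10.1 × √(2/100) = 1.4 days. This is already part of the unadjusted standard error above.

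**If transfers counted as discharge (not stated in the documents).** Leaving at 28+0 instead of 35+0 is 49 days earlier. With 30% to 50% of infants transferred at exactly 28+0 (both assumed), the added SD is 49 × √(p(1 − p)) = 22 to 24.5 days. Power for the same 5 days would be 22% to 24% at r = 14 and 24% to 26% at r = 10. This is a worst case, because 28+0 is the earliest usual time and not a fixed date.

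**The case against.** The strongest reply is that this is only a missing definition. Age could be meant as postmenstrual, the scale on which the protocol itself gives discharge timing, and then gestational age at birth drops out. The Cox sentence mentions adjustment for gestational age and is not expressly confined to time to full feeds. Gestational age and region precede randomisation, and the protocol says that transfer decisions "will only be based on current criteria and will not be affected by the participation in the study", so there is no bias. The effect size and SDs above are assumed.

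Most of this is right and limits the point. The absence of bias stands fully. The postmenstrual reading is possible, but nothing in the plan selects it. The Cox sentence cannot be relied on for this outcome: it follows the time-to-full-feeds test and names no other outcome, while the general rule for numerical values is unadjusted.

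Two stronger readings should be resisted. A reader might infer that the outcome mainly measures gestational age at birth, so that any treatment effect is swamped. That would need other variation with an SD below about 8 to 10 days, which the documents do not give; at 14 days the share is about a third. A reader might also infer that leaving Uppsala by transfer is counted as discharge, so that home region dominates. Follow-up keeps discharge home and transfer apart and obtains data from receiving hospitals, so the text leaves this open and does not state such a rule.

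**Conclusion.** The point holds as a minor loss of precision combined with an incomplete definition. On the postnatal reading with discharge home as the event, leaving gestational age in the variance costs roughly 18 percentage points of power at an other-variation SD of 14 days (71% − 53%), 24 points at SD 10 (94% − 70%) and 6 points at SD 21 (39% − 33%). These figures rest on an assumed 5-day effect, uniform gestational ages, 100 infants per arm and the assumed SDs. The 34-day spread follows directly from the protocol's own dates, taking 35+0 as the common discharge point. The comparison remains valid, and the primary outcomes are unaffected. A much larger loss would arise only if transfers were treated as discharges, which the plan does not say.

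**What to change.** - In Secondary outcomes, define the outcome as postmenstrual age at final discharge home, from whichever hospital, and state that transfer to a home hospital unit is not discharge. Alternatively, keep postnatal age at discharge home and name an analysis adjusted for gestational age at birth. The two are nearly equivalent if infants go home at about one postmenstrual age.
- In Follow-up, add the date of discharge home to the items obtained from receiving hospitals.
- State how infants who die before discharge are handled, since they have no value for this outcome and mortality is itself a listed secondary outcome.

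The cost is some wording and one extra date per transferred infant, from hospitals the investigators already plan to contact. Gestational age at birth is known for every infant from eligibility. One limitation remains: receiving hospitals' own discharge practices will still add some variation.
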